# 2. BIOLOGICAL RESEARCH OBJECTIVES

AstraZeneca and Bristol-Myers Squibb desire the opportunity to study the effects of treatment with saxagliptin on changes in biomarkers in patients with type type 2 diabetes and either established atherosclerotic disease or multiple risk factors, with the following possible objectives:

- Evaluate the effect of treatment with saxagliptin compared to placebo on the change in baseline biomarkers of inflammation, thrombosis, atherogenesis, metabolism, hemodynamic stress and myocardial injury
- Evaluate the interaction between baseline biomarkers of inflammation, thrombosis, atherogenesis, metabolism, hemodynamic stress and myocardial injury with the clinical efficacy of saxagliptin
- Prospectively evaluate the prognostic efficacy of a multimarker approach to risk assessment utilising baseline levels of inflammation, ventricular stress, myocardial necrosis and metabolic dysregulation.
- Evaluate the prognostic performance of other established and novel plasma/serum markers of inflammation, endothelial function, oxidative stress, hemodynamic stress, ischaemia/necrosis, metabolic dysregulation and renal dysfunction alone and in combination for clinical outcomes
- Assess the change in these biomarkers over time in a population with a history of diabetes

As such, the following list of biomarkers is proposed at this time. The entire list may not be studied, or additional biomarkers may be added as knowledge in the field develops, as deemed appropriate by the Executive Committee.

Biomarkers of Inflammation and Atherogenesis

- hs-CRP
- metalloproteinases (PAPP-A, MMP-9, MMP-11, cathepsins, myeloperoxidase)
- cytokines (IL-1β, IL-1Ra, IL-6, IL-18)
- chemotactic molecules (MCP-1, CCR1, CCR2)
- placental growth factor and soluble Flt-1

### Biomarkers of Endothelial Function

• vWF, E-selectin, VCAM-1, ICAM-1

### Biomarkers of Thrombosis

• tissue factor, sCD40L, prothrombin fragment 1.2, thrombin precursor protein

### Biomarkers of Oxidative Stress

- oxidized amino acids, oxidized apoA1,
- ADMA and other arginine metabolism products,
- secretory phospholipase,
- LpPLA2

Biomarkers of Ischaemia/Necrosis

• high-sensitivity cardiac troponin, malondialdehyde-modified low-density lipoprotein

Glycation end products and associated receptors

• AGE, sRAGE, RAGE

Biomarkers of Hemodynamic Stress

• BNP/NT-proBNP, ST-2, Copeptin

Biomarker of Metabolic/Lipid Dysregulation

• Adiponectin, leptin, resistin, c-peptide, red blood cell phospholipid fatty acids (EPA and DHA

Biomarker of Renal Dysfunction

• cystatin-C

# **3. BIOLOGICAL RESEARCH PLAN AND PROCEDURES**

# **3.1** Selection of biological research population

This appendix to the Clinical Study Protocol has been subjected to peer review according to AstraZeneca and Bristol-Myers Squibb standard procedures.

The patient will be asked to participate in this biological research at Visit 1. If the patient agrees to participate, a blood sample will be taken for biological research at Visit 1 (baseline) and at Visit 5 (24 months) or at the End of Treatment visit in case of premature discontinuation of IP or if patient has not had a Visit 5 sample drawn at time of study closure.

# 3.1.1 Study selection record

All patients will be asked to participate in this biological research. Participation is voluntary and if a patient declines to participate there will be no penalty or loss of benefit. The patient will not be excluded from any aspect of the main study.

# 3.1.2 Inclusion criteria

For inclusion in this biological research, patients must fulfil all of the inclusion criteria described in the main body of the Clinical Study Protocol **and**:

• Provide informed consent for the biological sampling and analyses.

# 3.1.3 Exclusion criteria

Exclusion from this biological research may be for any of the exclusion criteria specified in the main study.

### **3.1.4** Discontinuation of patients from this biological research

Specific reasons for discontinuing a patient from this biological research are:

Withdrawal of consent for biological research: Patients may withdraw from this biological research at any time, independent of any decision concerning participation in other aspects of the main study. Voluntary discontinuation will not prejudice further treatment. Procedures for discontinuation are outlined in Section 7.8 of the main Clinical Study Protocol.

# **3.2** Collection of samples for biological research

A blood sample (6 mL EDTA-anticoagulated, 6 mL serum tubes) will be taken at baseline and month 24 in all randomised patients. Detailed procedures are described in the Laboratory Manual.

The biomarker samples will be labelled (or "coded") with a study specific code. Samples do not carry any patient identifying information.

Careful separation of plasma and serum will be performed on site and stored at -20°C or colder until shipped to the central laboratory on dry ice, where samples will be stored at -70°C or colder until thawed for analysis. Samples will be shipped to **Biobanken Mölndal**, **AstraZeneca R&D** (intermediate storage) for subsequent transfer to the (TIMI) Biomarker Core Lab (Boston, MA) for analysis.

In addition to analysis of biomarkers of necrosis/ischaemia, inflammation, and coagulation listed above, proteomics analysis may be performed to develop and test novel protein markers of inflammation and coagulation.

# **3.3** Coding and storage of samples

The processes adopted for the coding and storage of samples for biological analysis are important to maintain patient confidentiality. Samples will be stored for a maximum of 15 years, from the date of last patient last visit, after which they will be destroyed. Samples will be stored and used until no further analyses are possible or the maximum storage time has been reached.

# 4. ETHICAL AND REGULATORY REQUIREMENTS

The principles for ethical and regulatory requirements for the study, including this biological research component, are outlined in Section 8 of the main Clinical Study Protocol.

# 4.1 Informed consent

The biological component of this study is optional and the patient may participate in other components of the main study without participating in the biological component. To participate in the biological component of the study, the patient must sign and date both the consent form for the main study and the biological component of the study. Copies of both signed and dated consent forms must be given to the patient and the original filed at the study centre. The principal investigator(s) is responsible for ensuring that consent is given freely and that the patient understands that he/she may freely discontinue from the biological aspect of the study at any time.

# 4.2 Patient data protection

Bristol-Myers Squibb or AstraZeneca will not provide individual results to patients, any insurance company, any employer, their family members, general physician or any other third party, unless required to do so by law.

Extra precautions are taken to preserve confidentiality and prevent biological data being linked to the identity of the patient. In exceptional circumstances, however, certain individuals might see both the biological data and the personal identifiers of a patient. For example, in the case of a medical emergency, a Bristol-Myers Squibb and/or an AstraZeneca physician or an investigator might know a patient's identity and also have access to his or her biological data. Also Regulatory authorities may require access to the relevant files, though the patient's medical information and the biological files would remain physically separate.

# 5. DATA MANAGEMENT

Biomarker data from the TIMI Biomarker Core Lab will be merged with the clinical database for statistical analysis.

The results from this biological research will be reported in a CSR Amendment/Errata/Scientific Report or Scientific Publication.

Some or all of the clinical datasets from the main study may be merged with the biological data in a suitable secure environment separate from the clinical database.

# 6. STATISTICAL METHODS AND DETERMINATION OF SAMPLE SIZE

The number of patients who will agree to participate in the biological research is unknown. It is therefore not possible to establish whether sufficient data will be collected to allow a formal statistical evaluation or whether only descriptive statistics will be generated.

Biomarker data from the TIMI Biomarker Core Lab will be merged with the clinical database for statistical analysis. Analyses will be for exploratory purposes. Correlation between serum/plasma markers and outcomes will be analysed with the marker data both as continuous and categorical variables. Clinical outcomes examined will include the primary efficacy endpoint, and major secondary endpoint, the composite of cardiovascular death or myocardial infarction, the composite of cardiovascular death and heart failure, progression and complications of diabetes, as well as each element individually. Additional analyses will be performed to assess the effect of saxagliptin on the change in biomarkers from baseline 24 months. In addition, analyses to test for interaction between the effect of saxagliptin and baseline biomarkers will be performed using stratified analyses as well as logistic regression with the main effects and an interaction term. A statistical analysis plan will be prepared where appropriate.

# **1 EVENTS OF SPECIAL INTEREST**

The Medical Dictionary for Regulatory Activities (MedDRA) Version 12.0 is used for the definitions of the events of special interest and is subject to updates.

# **2** DECREASE IN LYMPHOCYTE OR THROMBOCYTE COUNTS

Adverse events related to decrease in lymphocyte and thrombocyte counts will be identified using the following MedDRA preferred terms (PTs).

### **PTs for Lymphopenia:**

Lymphopenia

Lymphocyte count decreased

Lymphocyte percentage decreased

B-lymphocyte count decreased

T-Lymphocyte count decreased

CD4 lymphocytes decreased

CD8 lymphocytes decreased

# PTs for Thrombocytopenia:

Autoimmune Thrombocytopenia

Haemolytic uraemic syndrome

Idiopathic thrombocytopenic purpura

Platelet count decreased

Platelet destruction increased

Platelet production decreased

Plateletcrit decreased

Thrombocytopenia

Thrombocytopenic purpura

Thrombotic thrombocytopenic purpura

# **3 SEVERE INFECTIONS**

Adverse events related to severe infections will be identified by meeting (a) and (b)

- (a) All MedDRA PTs fall under the **system** organ class of infections and infestations
- (b) The event meets the regulatory criteria for seriousness (eg, hospitalisation)

# **4 OPPORTUNISTIC INFECTIONS**

The medical concept for this list of PTs of infections includes all those that appear on the 1993 CDC List of AIDS-Defining Diagnoses, and that are specific for immunosuppression.

The following is a breakdown of the Preferred Terms in the list, by organism category and organism.

Organism category	Organism
Bacteria	Listeria
	MAC
	Mycobacterial
	Salmonella sepsis
	Tuberculosis
	Tubo-ovarian abscess
	Bacillary angiomatosis/Bartonellosis
Fungus	Coccidioides
	Cryptococcus
	Histoplasmosis
	Pneumocystis
	Fungal (esophageal, neurological, systemic or visceral)
	Candida (esophageal, neurological, systemic or visceral)
Protoza	Cryptosporidia
	Isospora
	Toxoplasmosis
Virus	CMV
	HSV (esophageal, neurologic, systemic or visceral)
	Herpes Zoster (multidermatomal, neurological or disseminated)
	JC Virus, PML
Opportunistic infection (unspecified)	Opportunistic infection (unspecified)

Opportunistic infections will be identified using the following MedDRA PTs:

Acute pulmonary histoplasmosis

Adrenal gland tuberculosis

Arthritis fungal

Atypical mycobacterial infection

Atypical mycobacterial lymphadenitis

Atypical mycobacterium pericarditis

Bacillary angiomatosis

Bartonellosis

Biliary tract Infection cryptosporidial

Biliary tract infection fungal

Bone tuberculosis

Bovine tuberculosis

Bronchitis fungal

Candida osteomyelitis

Candida pneumonia

Candida sepsis

Cerebral fungal infection

Cerebral toxoplasmosis

Chronic pulmonary histoplasmosis

Coccidioides encephalitis

Coccidioidomycosis

Congenital tuberculosis

Conjunctivitis tuberculous

Clinical Study Protocol Appendix I Drug Substance Saxagliptin Study Code D1680C00003 Edition Number 2.0 Date Cryptococcal cutaneous infection

Cryptococcal fungaemia

Cryptococcosis

Cryptosporidiosis infection

Cutaneous coccidioidomycosis

Cutaneous tuberculosis

Cytomegalovirus antigen positive

Cytomegalovirus chorioretinitis

Cytomegalovirus colitis

Cytomegalovirus duodenitis

Cytomegalovirus enteritis

Cytomegalovirus enterocolitis

Cytomegalovirus gastritis

Cytomegalovirus gastroenteritis

Cytomegalovirus gastrointestinal infection

Cytomegalovirus hepatitis

Cytomegalovirus infection

Cytomegalovirus mononucleosis

Cytomegalovirus mucocutaneous ulcer

Cytomegalovirus myelomeningoradiculitis

Cytomegalovirus myocarditis

Cytomegalovirus oesophagitis

Cytomegalovirus pancreatitis

Cytomegalovirus pericarditis

Cytomegalovirus proctocolitis

Cytomegalovirus syndrome

Cytomegalovirus test positive

Cytomegalovirus urinary tract infection

Cytomegalovirus viraemia

Disseminated cryptococcosis

Disseminated cytomegaloviral infection

Disseminated tuberculosis

Ear tuberculosis

Encephalitis cytomegalovirus

Encephalitis fungal

Endocarditis candida

Endocarditis histoplasma

Enterocolitis fungal

Epididymitis tuberculous

Extrapulmonary tuberculosis

Eye infection toxoplasmal

Female genital tract tuberculosis

Fungal abscess central nervous system

Fungal cystitis

Fungal endocarditis

Fungal oesophagitis

Fungal peritonitis

Fungal retinitis

Fungal rhinitis

Fungal sepsis

Gastritis fungal

Gastroenteritis cryptococcal

Gastroenteritis cryptosporidial

Gastrointestinal fungal infection

Hepatic candidiasis

Hepatic infection fungal

Hepatitis toxoplasmal

Herpes oesophagitis

Herpes sepsis

Herpes simplex hepatitis

Herpes simplex visceral

Herpes zoster disseminated

Herpes zoster infection neurological

Herpes zoster multi-dermatomal

Histoplasmosis

Histoplasmosis cutaneous

Histoplasmosis disseminated

Isosporiasis

JC virus infection

Joint tuberculosis

Listeria encephalitis

Listeria sepsis

Listeriosis

Lower respiratory tract infection fungal

Lymph node tuberculosis

Lymphadenitis fungal

Male genital tract tuberculosis

Meningitis candida

Meningitis coccidioides

Meningitis cryptococcal

Meningitis fungal

Meningitis herpes

Meningitis histoplasma

Meningitis listeria

Meningitis toxoplasmal

Meningitis tuberculous

Mycobacterial infection

Mycobacterium abscessus infection

Mycobacterium avium complex immune restoration disease

Mycobacterium avium complex infection

Mycobacterium chelonei infection

Mycobacterium fortuitum infection

Mycobacterium kansasii infection

Mycobacterium kansasii pneumonia

Mycobacterium marinum infection

Mycobacterium ulcerans infection

Necrotising fasciitis fungal

Neurocryptococcosis

Oesophageal candidiasis

Oesophageal tuberculosis

Opportunistic infection

Osteomyelitis fungal

Pancreatitis fungal

Pericarditis fungal

Pericarditis histoplasma

Pericarditis tuberculous

Peritoneal tuberculosis

Pneumocystis jiroveci infection

Pneumocystis jiroveci pneumonia

Pneumonia cryptococcal

Pneumonia cytomegaloviral

Pneumonia fungal

Pneumonia toxoplasmal

Presumed ocular histoplasmosis syndrome

Progressive multifocal leukoencephalopathy

Prostatitis tuberculous

Pulmonary tuberculoma

Pulmonary tuberculosis

Pyelonephritis fungal

Clinical Study Protocol Appendix I Drug Substance Saxagliptin Study Code D1680C00003 Edition Number 2.0 Date Renal tuberculosis Retinitis histoplasma Salmonella bacteraemia Salmonella sepsis Salpingitis tuberculous Silicotuberculosis Sinusitis fungal Spleen tuberculosis Splenic infection fungal Systemic candida Thyroid tuberculosis Toxoplasmosis Tuberculoma of central nervous system Tuberculosis Tuberculosis bladder Tuberculosis gastrointestinal Tuberculosis liver Tuberculosis of central nervous system Tuberculosis of eye Tuberculosis of genitourinary system Tuberculosis of intrathoracic lymph nodes Tuberculosis of peripheral lymph nodes Tuberculosis serology test positive Tuberculosis test positive

Tuberculous abscess central nervous system

Tuberculous laryngitis

Tuberculous pleurisy

Tuberculous tenosynovitis

Tubo-ovarian abscess

Urine cytomegalovirus positive

# **5 HYPERSENSITIVITY REACTIONS**

Hypersensitivity adverse events will be identified using the following MedDRA PTs:

Allergic oedema

Anaphylactic reaction

Anaphylactic shock

Anaphylactoid reaction

Anaphylactoid shock

Angioedema

Auricular swelling

Bronchial oedema

Circumoral oedema

Conjunctival oedema

Drug hypersensitivity

Endotracheal intubation

Epiglottic oedema

Eye oedema

Eye swelling

Eyelid oedema

Face oedema

Gastrointestinal oedema

Genital swelling

Gingival oedema

Gingival swelling

Gleich's syndrome

Hereditary angioedema

Hypersensitivity

Idiopathic urticaria

Intubation

Laryngeal dyspnoea

Laryngeal obstruction

Laryngeal oedema

Laryngospasm

Laryngotracheal oedema

Lip oedema

Lip swelling

Nasal oedema

Oedema genital

Oedema mouth

Oedema mucosal

Oral allergy syndrome

Orbital oedema

Oropharyngeal spasm

Oropharyngeal swelling

Palatal oedema

Penile oedema

Penile swelling

Periorbital oedema

Pharyngeal oedema

Scrotal oedema

Scrotal swelling

Small bowel angioedema

Stridor

Swelling face

Swollen tongue

Throat tightness

Tongue oedema

Tracheal obstruction

Tracheal oedema

Tracheostomy

Type I hypersensitivity

Urticaria

Urticaria cholinergic

Urticaria chronic

Urticaria papular

Vaginal oedema

Vaginal swelling

Visceral oedema

Vulval oedema

# **6 LIVER ABNORMALITIES**

### Detection of liver test abnormalities accompanied by jaundice or hyperbilirubinemia

- (a) Laboratory criteria will include: all cases with the following two criteria in the same sample:
  - i) ALT or AST elevated  $\geq$  3 times ULN

AND

- ii) Total bilirubin > 2 times ULN
- (b) Criteria by adverse event submissions will include:

Liver test abnormalities accompanied by jaundice or hyperbilirubinemia- a combination of at least one PT from column A and at least one PT from column B below. The MedDRA version is 12.1.

A (transaminase elevation)	B (bilirubin elevation, or jaundice)
Alanine aminotransferase abnormal	Hyperbilirubinaemia
Alanine aminotransferase increased	Icterus index increased
Aspartate aminotransferase abnormal	Jaundice
Aspartate aminotransferase increased	Jaundice cholestatic
Gamma-glutamyltransferase abnormal	Jaundice hepatocellular
Gamma-glutamyltransferase increased	Ocular icterus
Hepatic enzyme abnormal	Yellow skin
Hepatic enzyme increased	Bilirubin conjugated abnormal
Hepatic function abnormal	Bilirubin conjugated increased
Hypertransaminasaemia	Blood bilirubin abnormal

Liver function test abnormal	Blood bilirubin increased
Mitochondrial aspartate aminotransferase increased	Blood bilirubin unconjugated increased
Transaminases abnormal	Urine bilirubin increased
Transaminases increased	Urobilin urine present

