# 5.8 Discontinuation of investigational product

Patients may be discontinued from IP in the following situations:

- Voluntary discontinuation by the patient who is at any time free to discontinue treatment, without prejudice to further treatment
- Safety reasons as judged by the Investigator, by AstraZeneca, BMS and/or a representative.

Study-specific discontinuation criteria are listed below:

- Increase of ALT and/or AST >3 times the upper limit of normal (ULN) **and** increase of TB >1.5 times ULN confirmed at a repeated measurement within 4 days
- Increase of ALT or AST >10 times ULN confirmed at a repeated measurement within 4 days
- Pregnancy (discontinue IP and notify AstraZeneca or its representative), see Section 13.3

Cases where patients are incorrectly randomised (ie, the patient does not meet the required inclusion/exclusion criteria for the study), should be discussed with TIMI Study Group representative prior to any actions being taken (see Section 5.3).

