# 6.4.1.1 AEs of special interest

Secondary objectives will include an assessment of the long-term effects of saxagliptin on the following AEs of special interest: decrease in lymphocyte counts, decrease in thrombocyte counts, the risk of severe infections, hypersensitivity reactions, liver abnormalities, bone fractures, pancreatitis, skin reactions and renal abnormalities. For hypersensitivity reactions, especially angioedema, reports will include detailed information on concomitant use of an angiotensin-converting enzyme inhibitor or an angiotensin-receptor blocker. For cases of pancreatitis, serum lipase and/or amylase concentrations with accompanying normal ranges and any imaging study reports will be included in the narratives.

Specific clinical details for decrease in lymphocyte counts or thrombocyte counts, severe infections, hypersensitivity reactions, liver abnormalities, skin reactions and renal

abnormalities, bone fractures, pancreatitis, opportunistic infections and liver abnormalities with serum AST or ALT greater than or equal to 3 times ULN and serum TB greater than 2 times ULN or evidence of jaundice will be captured in supplemental CRF pages regardless of seriousness.

See Appendix I for information on identification of AEs of special interest.

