#### AEs based on signs and symptoms

All AEs spontaneously reported by the patient or reported in response to the open question from the study personnel: "Have you had any health problems since the previous visit?" or revealed by observation will be collected and recorded in the CRF. When collecting AEs, recording diagnoses is preferred (when possible) to recording a list of signs and symptoms. However, if a diagnosis is known and there are other signs or symptoms that are not generally part of the diagnosis, the diagnosis and each sign or symptom will be recorded separately.

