#### AEs based on examinations and tests

The results from protocol-mandated laboratory tests and vital signs will be summarised in the Clinical Study Report (CSR). Deterioration as compared to baseline in protocol-mandated laboratory values, vital signs and other safety variables should therefore only be reported as AEs if they fulfil any of the SAE criteria or are the reason for discontinuation of treatment with the IP.

If deterioration in a laboratory value/vital sign is associated with clinical signs and symptoms, the sign or symptom will be reported as an AE and the associated laboratory result/vital sign will be considered as additional information. Wherever possible; the reporting Investigator uses the clinical, rather than the laboratory term (eg, anaemia vs low haemoglobin value). In the absence of clinical signs or symptoms, clinically relevant deteriorations in non- mandated parameters should be reported as AE(s).

Any new or aggravated clinically relevant abnormal medical finding at a physical examination as compared with the baseline assessment will be reported as an AE.

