#### 12.1.3.5 Safety endpoints

Safety is evaluated by the following endpoints:

• Secondary safety endpoints:

- Incidence of overall AEs and AEs of special interest
- Other safety endpoints:
  - Changes from baseline in laboratory tests, pulse, BP, waist circumference and body weight
  - Incidence of hypoglycaemic events, cancers and peripheral oedemas

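### Appendix I identifies the liver special-interest event only by combined transaminase and bilirubin evidence, so some patients who meet a section 5.8 liver criterion, and some diagnosed hepatic cases, are not counted in it

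*Protocol*

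**What the plan says.** Protocol section 12.1.3.5 lists as a secondary safety endpoint the "Incidence of overall AEs and AEs of special interest". Liver abnormalities are one of these events (sections 2.3.1 and 6.4.1.1), and section 6.4.1.1 directs the reader elsewhere for the definition: "See Appendix I for information on identification of AEs of special interest".

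Appendix I section 6 has a single subheading, "Detection of liver test abnormalities accompanied by jaundice or hyperbilirubinemia", and two routes under it:

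- Route (a), laboratory: ALT or AST at least 3 times ULN and TB above 2 times ULN, both in the same sample.
- Route (b), adverse event terms: "a combination of at least one PT from column A and at least one PT from column B below". Column A holds transaminase and liver-test terms; column B holds bilirubin and jaundice terms.

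Section 5.8 has two liver criteria for discontinuing investigational product. The first is ALT and/or AST above 3 times ULN with TB above 1.5 times ULN, confirmed on repeat. The second has no bilirubin condition: "Increase of ALT or AST >10 times ULN confirmed at a repeated measurement within 4 days".

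Section 6.4.3 governs what reaches the adverse event database. It says that "recording diagnoses is preferred (when possible) to recording a list of signs and symptoms" and that, wherever possible, the investigator "uses the clinical, rather than the laboratory term". A deterioration in a protocol-mandated laboratory value is reported as an adverse event only if it meets a seriousness criterion or is the reason for stopping treatment.

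**The concern.** The endpoint carries a broad name and a narrow definition. The protocol regards two laboratory patterns as grave enough to stop treatment, yet one of them needs no raised bilirubin and the other uses a lower bilirubin cut-off than route (a). The recording rules steer sites towards a diagnosis, while route (b) searches mainly for paired laboratory-type terms.

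Section 6.4.1.1 also suggests that the general concept is meant to be wider than the combination. Its list for supplemental CRF pages names liver abnormalities in general and then adds, as a further item, "abnormalities, bone fractures, pancreatitis, opportunistic infections and liver abnormalities with serum AST or ALT greater than or equal to 3 times ULN" together with raised bilirubin or jaundice. Appendix I identifies only that further item.

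At stake is whether the between-arm incidence reported under the name liver abnormalities covers hepatocellular injury without marked bilirubin elevation, and hepatic disease recorded as a diagnosis.

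**Working it through.** No sample size, power or alpha figure is involved. The check sets the rules side by side and runs test cases through them.

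**Laboratory route.** Let A be ALT or AST and B be TB, both as multiples of ULN.

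- Section 5.8 criterion met, once confirmed: (A > 3 and B > 1.5) or A > 10.
- Route (a) met: A ≥ 3 and B > 2 in the same sample.

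Every patient who meets section 5.8 has A > 3, so the transaminase part of route (a) is always satisfied and the outcome depends on B alone. Patients meeting section 5.8 but not route (a) are those with B ≤ 2, that is (A > 3 and 1.5 < B ≤ 2) or (A > 10 and B ≤ 2).

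| A (× ULN) | B (× ULN) | Section 5.8 met | Route (a) met |
|---|---|---|---|
| 3.5 | 1.6 | yes | no |
| 5 | 1.9 | yes | no |
| 5 | 2.0 | yes | no |
| 5 | 2.1 | yes | yes |
| 9 | 1.0 | no | no |
| 11 | 1.0 | yes | no |
| 12 | 1.8 | yes | no |
| 15 | 1.4 | yes | no |
| 12 | 2.5 | yes | yes |

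**Adverse event route.** Each column has 14 preferred terms, 14 + 14 = 28 in all. A search of the 28 for hepatitis, failure, necrosis, cirrhosis, injury and toxic terms finds none.

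| Terms recorded | Route (b) met |
|---|---|
| Alanine aminotransferase increased | no |
| Jaundice | no |
| Hepatitis | no |
| Hepatitis and Jaundice | no |
| Alanine aminotransferase increased and Blood bilirubin increased | yes |

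**Putting the two routes together.**

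1. *Confirmed ALT or AST above 10 times ULN, TB not above 2 times ULN.* Route (a) fails. Section 6.4.3 lets the transaminase rise be an adverse event when it is the reason for stopping, but that supplies a column A term only. The patient is not counted unless a bilirubin or jaundice event is recorded as well.
2. *ALT/AST above 3 times ULN, TB above 1.5 and up to 2 times ULN.* Route (a) fails. Both raised values together form the reason for stopping, so both may be recorded, and then route (b) is met. If only one is recorded, the patient is not counted.
3. *Hepatic diagnosis only.* Under section 6.4.3, signs that usually belong to a diagnosis need not be listed separately. A lone hepatitis or hepatic failure term fails route (b), and adding jaundice does not help because column A is still empty. The patient is counted only if a sample meets route (a).

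**Neighbouring sections of Appendix I.** Pancreatitis (section 8) is identified by any one listed term, including the diagnosis itself. Renal abnormalities (section 10) are identified by laboratory change and/or a single term such as renal failure. Only the liver section demands two kinds of evidence at once and lists no organ diagnosis of the types searched.

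**The case against.** The strongest reply is that the combination is deliberate. The subheading states its purpose, and section 6.4.2 uses the same laboratory pairing for expedited reporting. A stopping threshold and an event-identification threshold serve different ends and need not agree. Section 6 says that its criteria will include the two routes, Appendix I calls its definitions open to update, and an SAP could add searches. The repeated mention of liver abnormalities in section 6.4.1.1 may be no more than loose drafting.

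Much of this is fair. A specific combined event is worth having, and differing thresholds are not an error in themselves. The section 6.4.1.1 wording is supporting evidence, not proof. But the protocol fixes identification in Appendix I, and nothing in the open-ended wording adds the missing cases.

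Three stronger readings are tempting and are not supported:

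- *That patients stopped for liver reasons are, as a class, not counted.* Those with TB above 2 times ULN in the same sample are counted by route (a), including those with ALT above 10 times ULN. Others are counted by route (b) when both kinds of term are recorded.
- *That a hepatic excess would be reported as no signal.* Section 12.2.2 summarises by arm all adverse events, changes in each laboratory test and predefined marked abnormalities. Section 6.4.1.1 requires supplemental pages for liver abnormalities regardless of seriousness, section 11.2.2 provides expert review for other significant events, and the DMC sees unblinded data. An excess could be seen there.
- *That yearly liver tests mean most acute cases escape the laboratory route.* Any such figure needs an assumed episode length, which the protocol does not give, and it ignores unscheduled, repeat and end-of-treatment samples. It cannot apply to patients meeting section 5.8, who by definition have an abnormal sample and a confirming one.

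**Conclusion.** The point holds in limited form. As defined, the liver event omits patients with confirmed ALT or AST above 10 times ULN and TB not above 2 times ULN who have no bilirubin or jaundice event. It omits patients with ALT/AST above 3 times ULN and TB above 1.5 and up to 2 times ULN unless both abnormalities are recorded as events. It also omits cases coded only as a hepatic diagnosis with no sample meeting route (a).

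The incidence by arm under the name liver abnormalities would therefore be incomplete. How many patients this affects cannot be derived, because the protocol gives no expected liver event rates. The conclusion rests on reading the two routes as the whole definition, which is how the text stands.

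The result is descriptive, one of nine special-interest categories in section 2.3.1, with no test or alpha attached. The primary analysis is untouched. This is a cheap improvement to a secondary safety result. No view is taken on which clinical threshold is right, only that sections 5.8, 6.4.1.1 and 6.4.3 and Appendix I section 6 should be reconciled.

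**What to change.** In Appendix I section 6, define the liver event as any of the following:

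- the present combination, by route (a) or route (b);
- any laboratory result that meets an existing section 5.8 liver criterion;
- any preferred term that is itself a hepatic diagnosis, for example hepatitis, liver injury, hepatic necrosis or hepatic failure, with the terms listed.

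Keep the present combination as a named subset, and report the total and the subset by arm. No discontinuation threshold is changed.

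The cost is a revision of the Appendix I wording and a wider search of data already being collected. The reported incidence will be higher in both arms and the wider event less specific; keeping the subset preserves the specific result.
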